### **I. Abstract - Summary of the study background, aims, and design.**

Central themes in person-centered care are dignity/respect/choice for the care recipient.

This SBIR Phase 1 clinical study is a minimal risk study that focuses on how the new technology, DevaWorld (DW), can support and amplify these principles, while assisting care staff.

DevaWorld is an interactive assistive technology developed with user-centered design principles, mirroring fifteen evidence-based non-pharmacological interventions for people living with Alzheimer's disease and its related dementias (AD/ADRD). Built with a game engine and deployed on a tablet device, DevaWorld is a purpose-built virtual world depicting activities of daily living (ADLs). It contains interactive engagement stimuli, including customized digital artifacts that hold meaning to the person.

During a DevaWorld session (DWS), both the care-partner and care-receiver (dyad) are active participants. Preliminary evidence shows that DWS sessions support the psychosocial wellbeing of people living with dementia (PLWD). Informally collected data lead us to the current study, in which we measure the impact of DevaWorld ADLs on actual ADLs. We hypothesize that undertaking ADL-related virtual activities will support completions of actual ADLs, thereby increasing effectiveness and improving care outcomes.

The aims of this mixed-method, single-arm study are to (1) demonstrate the feasibility (tolerability and acceptability) of DevaWorld within daily routines, and (2) evaluate the effectiveness of DevaWorld sessions in preparing PLWD for specified ADLs. Endpoints are: evidence of the dyads' acceptance of DevaWorld, a reduction in ADL-related care challenges compared to baseline, and overall durations of time spent on the ADLs compared to baseline.

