##### *d. Study outcomes/endpoints*

The study outcome will be a body of evidence that supports our hypothesis: that interactions with ADL content inside the graphical interactive virtual world, DevaWorld, supports completions of actual ADLs.

DevaWorld's feasibility (Aim 1)

Successful primary outcomes are >55% DWS-participation rate and a statistically significant difference between assessments of DWS-participation and non-participation, indicating tolerability and acceptability of routine DWS.

DevaWorld as an assistive tool for preparing and completing ADLs. (Aim2)

Successful secondary outcomes are:

- a reduction in ADL-related care challenges compared to baseline
- reduced time spent on ADLs compared to baseline
- a reduction in negative response behaviors associated with the ADL
- greater interest in the ADL
- a positive shift in care staff attitudes

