nor exclude participation based on cognitive test scores, however, participants will be given the MMSE test (20) at baseline. Anonymized scores may be referenced in post-study discussions. The participants will have had challenge(s) completing one or more ADLs in the previous month, as discussed at staff meetings, referenced in care plans, or observed/experienced by direct care staff. Ineligible residents are those with significant

non-AD/ADRD neurological, psychiatric, or physical impairment or those who are totally dependent upon others for ADLs.

Other specifications:

- Understand English or Russian.
- Are verbal
- Can sit comfortably for at least 15 minutes in a chair/wheelchair at a table or propped up in bed or princess chair with a tray table
- Are not known to be in pain
- Have good vision, or good corrected vision (i.e., glasses)
- Have good hearing, or good corrected hearing (i.e., aids)
- May sometimes have anxiety or agitation when undertaking ADLs.

Exclusion criteria

- Persons subject to a legal protection order
- Current or planned participation in other research involving neuropsychological evaluations and/or drug trial, up until the end of the current study.
- Informed consent not signed
- Compatible caregiver not found

Staff

Staff are experienced and motivated; are employed at the test site; assist with ADLs will have ADL care experience with residents prior to the study. Their role is to support the participant during a DWS and help them have an optimal session with the app. Staff will receive training on this. After the DWS, staff will assist the resident with their usual ADL routine at times suited to the resident. They will also fillout reports each day.

*ii. List and describe each of the study procedures, assessments, and activities.*

- Initiation session with staff to outline baseline study protocol.
- In the first two weeks of the study to establish baseline, dyads will undertake usual ADL care, i.e., without the DevaWorld Session (DWS) intervention. Staff schedule during baseline:

Mon 40m	Tue 40m	Wed 40m	Thu 40m	Fri 40m
Res A Mouth Care	Res A Mouth Care	Res A Mouth Care	Res A Mouth Care	Res A Mouth Care
Res B Mouth Care	Res B Mouth Care	Res B Mouth Care	Res B Mouth Care	Res B Mouth Care
Res C Mouth Care	Res C Mouth Care	Res C Mouth Care	Res C Mouth Care	Res C Mouth Care
Res Mouth Care	Res Mouth Care	Res Mouth Care	Res Mouth Care	Res Mouth Care
Reporting before end of shift				

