- Following baseline and prior to the intervention phase, participating staff will take part in group training, with extra support as needed.
- During the intervention phase, a period of six weeks, the same dyads (or as close to same as is practical) will be assigned a schedule incorporating DWS followed by the same ADL routine as baseline.
- Each resident-participant will have two DWS per week. Staff-participants will spread this load across their shifts, averaging eight DWS sessions per 5-day week. We anticipate that session durations will average five minutes with variability according to resident-participants' individual interest levels on a given day. Staff schedule during study:

Mon 1h 10m	Tue 55m	Wed 1h 10m	Thu 55m	Fri 1h 10m
Res A DWS	Res A Mouth Care	Res A DWS	Res A Mouth Care	Res A Mouth Care
	Res B Mouth Care		Res B DWS	Res B Mouth Care
Res A Mouth Care	Res C DWS	Res A Mouth Care		Res C DWS
Res B DWS		Res B Mouth Care	Res B Mouth Care	
Res C Mouth Care	Res C Mouth Care	Res C Mouth Care	Res C Mouth Care	
Res B Mouth Care	Res D Mouth Care	Res D DWS	Res D Mouth Care	Res D DWS
Res C Mouth Care				
Res D Mouth Care		Res D Mouth Care		Res D Mouth Care
Reporting				

- Procedure for running a DWS

- **Initiating a session:**

Prior to the ADL, the dyad will sit in a quiet nook or the resident's bedroom with appropriate lighting. The care staff will ask the resident if they are comfortable (e.g. need a drink, need to go to the toilet, is comfortably dressed, has glasses and hearing aids in place).

To initiate the session, the care staff will open DevaWorld on the tablet device and invite resident to join.

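### ADL completion is the hypothesis, but a completion question is listed only for baseline and no completion proportion is planned, so a change in ADL time cannot be read as speed alone

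*Combined protocol and SAP*

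**What the plan says.** All references are to the combined protocol and SAP.

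- **Hypothesis.** Section V.d states that interacting with ADL content in DevaWorld "supports completions of actual ADLs". Section III makes better ADL completion the primary objective. Section VI.c.i selects residents on the same problem: "The participants will have had challenge(s) completing one or more ADLs in the previous month".
- **Outcomes.** The Aim 2 list in Section V.d includes "a reduction in ADL-related care challenges compared to baseline" and "reduced time spent on ADLs compared to baseline". The Abstract gives the time endpoint as "overall durations of time spent on the ADLs compared to baseline". Section IX words it instead as the time needed to complete ADLs.
- **Daily survey.** Section VI.c.ii lists for baseline the start and stop times, a four-item ADL checklist and a separate question on whether the activity was completed. For the intervention phase it lists a checklist of which ADLs were done and the time to start and finish. Autonomy and attitude ratings (1 to 4) are listed in both phases.
- **Analysis.** Section IX says the outcome measures do not change between phases. The only completion rate it defines is the share of dyads who stay through all eight weeks. Its stated null hypothesis concerns ADL scores, and it tests the ADCS-ADL scores in total and by item.

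**The concern.** Completion is what the study sets out to change, yet the listed forms do not record it in the same way before and after the intervention starts. No planned outcome summarises it per occasion. Time is then left as the main occasion-level measure of the ADL itself, and time and completion are entangled. An ADL that is abandoned early is short. One that is resisted and then given up may be long, and Section VI.c.i says of eligible residents: "May sometimes have anxiety or agitation when undertaking ADLs". If the share of unfinished ADLs changes between phases, mean time changes even when nobody becomes faster or slower. In one unfavourable case, where unfinished ADLs are short and completion gets worse, mean time falls and the plan would count that as success.

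**Working it through.** The plan gives no completion rate, mean ADL time or effect size, so there is no stated figure to reproduce. The check is a comparison of the listed items, a count of occasions and an illustration.

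**1. Items side by side (Section VI.c.ii)**

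| | Baseline | Intervention |
|---|---|---|
| Which ADLs | four-item checklist | checklist of ADLs done |
| Completion | separate question | none listed |
| Time | start and stop | start and finish |
| Autonomy, attitude | 1 to 4 | 1 to 4 |

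Stopping covers an abandoned ADL; finishing need not. An unticked item in the intervention list could mean not attempted, refused or left unfinished.

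**2. Other planned measures that come near**

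- The completion rate in Section IX is retention of dyads, not completion of ADLs.
- The ADCS-ADL is a periodic score sheet, and Section IX notes that it covers more ADLs than DevaWorld depicts. It does not show whether a particular timed ADL was finished.
- The autonomy and attitude ratings are made in both phases, but they do not record completion.
- ADL-related care challenges could include completion, but no measure is assigned to them.

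**3. Occasions affected**

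The Section VI.c.ii schedules show an ADL routine on five days a week, and in the intervention phase a DWS is "followed by the same ADL routine as baseline". Using the target of 32 residents (Sections V.c and VI.a):

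- Baseline: 5 x 2 weeks = 10 per resident; 10 x 32 = up to 320 occasions with the completion question listed.
- Intervention, all days reported: 5 x 6 weeks = 30 per resident; 30 x 32 = up to 960 occasions without it.
- Intervention, only ADLs that follow a DWS (two a week): 2 x 6 x 32 = 384.

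The heading of the intervention list could mean the narrower set. Sections VI.c.i (staff report each day) and VI.c.iv (end-of-shift notes on days with and without the intervention) favour the wider one. The text does not settle it.

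**4. Effect on mean time with speed unchanged**

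Let p be the proportion of attempted ADLs completed and f the ratio of unfinished to finished time. Both are assumptions. Relative mean time over all attempts = p + (1 - p) x f.

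| f | p = 0.6 | p = 0.8 | 60% to 80% | 80% to 60% |
|---|---|---|---|---|
| 0.3 | 0.72 | 0.86 | +19.4% | -16.3% |
| 0.5 | 0.80 | 0.90 | +12.5% | -11.1% |
| 0.7 | 0.88 | 0.94 | +6.8% | -6.4% |
| 1.0 | 1.00 | 1.00 | 0% | 0% |
| 1.3 | 1.12 | 1.06 | -5.4% | +5.7% |

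For example, 0.86/0.72 = 1.194. With high completion and a small change, 95% to 98% at f = 0.5, the result is 0.990/0.975 = 1.015, or about +1.5%.

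**The case against.** The strongest reply is that this is a drafting difference. The survey bullets read like summaries, a daily tick list of ADLs done can itself indicate completion, and Section IX says the measures are the same in both phases. The plan also has comparisons that are like for like: the ADCS-ADL scores, which are the subject of its stated null hypothesis, and the daily ratings. Staff assist with ADLs and totally dependent residents are excluded, so completion may be high and the effect on mean time small. ADL time is a secondary outcome in a feasibility study.

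Much of this stands. A reader might infer that completion cannot be assessed at all in the intervention phase. The documents do not support that, because the checklist of ADLs done may be a partial proxy. A reader might also infer that the time outcome is biased towards success, or that the distortion is large. Neither follows: the sign depends on whether unfinished ADLs are shorter or longer than finished ones, the size depends on completion rates, and the documents give neither.

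What does not stand is that nothing needs changing. If the sentence in Section IX covers the survey, the lists contradict it. If it refers only to the score sheets mentioned next to it, nothing requires the survey items to match. Under either reading there is still no planned completion proportion and no rule for timing unfinished ADLs.

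**Conclusion.** The point holds as a gap that should be closed before data collection. As listed, the study cannot compare occasion-level ADL completion like for like between phases, and a change in mean ADL time may partly reflect a change in completion. The range of about -16% to +19% rests on an assumed 20-point swing and f between 0.3 and 1.3. It shrinks to about +1.5% for 95% to 98% at f = 0.5, and to zero if unfinished and finished ADLs take equally long. These figures show what is possible; they do not estimate a bias. If the form is used as listed, answers to a completion question that was not asked could not be reliably reconstructed later, except so far as the checklist stands in for them.

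**What to change.** 1. In Section VI.c.ii, list in the intervention survey the same completion question and the same start/stop wording as at baseline, and say that it is filled in on every ADL reporting day. Separate attempted and completed fields for each checklist item are not needed for this purpose.
2. In Sections V.d and IX, add one secondary outcome: the proportion of attempted ADL occasions that were completed. Name it so that it cannot be confused with the eight-week study completion rate. Compute it per resident and phase and compare within resident, for example with the Wilcoxon signed-rank test that Section IX already names for the ADCS-ADL. Show intervention days with and without a DWS separately as well as together, because on a five-day schedule with two DWS a week about three ADL days in five have no DWS.
3. Use one definition of ADL time in the Abstract, Section V.d and Section IX. A workable choice is time over all attempted ADLs, always reported beside the completion proportion.

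The cost is one extra question in each intervention report, a few lines of text and one more secondary outcome to interpret. Care, design and sample size are unchanged.

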Reliability  
A staff champion (internal) will be appointed to oversee adherence to the study and liaise with the research team about any obstacles they notice along the way, such as

absenteeism or the need for extra training. A research assistant (external), in the role of reliability observer, will be assigned to track data, checking for reporting compliance and anomalies. The PI will review data week-by-week to ensure the study design continues to fit its purpose.

- Data collected at Baseline

Residents

- **Demographic variables:** Gender, age, race, ethnicity, marital status, socioeconomic status, languages spoken/language preference.
- **Stage of dementia** The Global Deterioration Scale for Assessment of Primary Degenerative Dementia (GDS) (16)
- **Cognitive Function:** The Mini Mental State Exam (MMSE) (20).
- **Functional stage** (Functional Assessment Staging Tool (FAST), (22): The FAST is used to describe the stages of dementia and employs a seven-stage system based on one's level of functioning and ability to perform daily living activities.
- **Time since admission** to facility (in months) {subtract date of admission from date of assessment).
- **Quality of life:**  
-DEMQOL/DEMQOL-proxy (23).
- **Response Behaviors**  
- The Neuropsychiatric Inventory (NPI): Assessing psychopathology in dementia patients. (24).
- **ADL capacity**  
Alzheimer's Disease Cooperative Study Activities of Daily Living Inventory (ADCS-ADL) 19- item inventory to assess activities of daily living for clinical trials in Alzheimer's disease. (25).

Care Staff

- **Demographics:** Age, gender, race, ethnicity, number of years of schooling and highest degree obtained, US or foreign born; languages spoken/language preference, marital status, currently or previously the primary informal caregiver of a person with dementia (a predictor of job satisfaction (26). Job background: Years as a CNA, years working for this employer, employed full or part time.
- **Burnout:** Copenhagen Burnout Inventory (27).
- **Sense of Competence:** Sense of Competence in Dementia Care Staff (SCIDS) (28).
- **Attitudes towards People with Dementia:** Approaches to Dementia Questionnaire (ADQ) (29).
- **Job Satisfaction:** Minnesota Satisfaction Questionnaire, Short-form (30).

Baseline data for Usual ADLs – No Intervention

- Staff's usual reporting at the end of each shift.
- Additional: the survey webpage.
  - Subject name
  - Time: start of ADL and stop ADL

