  - ADL checklist: toothbrushing, grooming, face wiping, taking medications
  - Was the activity completed?
- Subject's responses to the ADLs (multiple choice and text box)
  - Subject's autonomy to the activity (Likert scale of 1- 4)
  - Subject's attitude to the activity (Likert scale of 1- 4)
- At the end of the baseline studies, staff complete an ADCS-ADL score sheet for

each of their residents to provide longitudinal comparisons (31).

- Data collected during the Intervention phase

Reporting on The DevaWorld App's Feasibility (Aim 1)

- The DW app captures screen interactions, durations, end-of-session emoticons for self-assessment and end-of-session comments (choice of spoken or text input).
- The tablet's built-in camera records the dyad's expressions and exchanges during the session. These videos support analysis of engagement and reaction, and create a unique data set for developing speech emotion recognition system for future product upgrades.
- Occasionally research staff may also capture video and audio using an iPhone during DWS for capturing other nuances of the dyad engagement.
- In addition, at end of shift, staff complete a web-based questionnaire that
  - measures tolerance and acceptance of DevaWorld
  - records observations of resident's post and pre-post disposition
- Questions are a mix of multiple choice, 5-point Likert scales and free text
- Computers are located at the nurse station.

Reporting on Usual ADLs, following Intervention (Aim 2)

- Staff's usual reporting at the end of each shift.
- Additional: the survey website.
  - Subject name
  - Which ADLs were done (checklist)?
  - Time taken to start and finish
- Subject's responses to the ADLs (multiple choice and text box)
  - Autonomy to the activity (Likert scale of 1- 4)
  - Attitude to the activity (Likert scale of 1- 4)
- End of study
  - Residents will repeat Quality of Life and Response Behavior outcome measures (same ones as used in Baseline).
  - Participating staff will complete an ADCS-ADL scores sheet for each of their residents to provide longitudinal comparisons
  - Participating staff will undertake a 5 min exit interview at the conclusion of the trial. The interview will supplement and facilitate the interpretation of quantitative data gathered during including any post and pre-post concerns over the course of the study, which may provide further insights (32).

*iii. Explain training of individuals performing procedures*

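### A shift in care staff attitudes is a listed secondary outcome, but the schedule gives the staff attitude scale at baseline only, so no paired attitude score will exist

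*Combined protocol and SAP*

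**What the plan says.** Section V.d lists "a positive shift in care staff attitudes" as one of five successful secondary outcomes under Aim 2. It names no instrument and does not say what the attitudes are towards.

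Section VI.c.ii lists four care staff scales among the baseline data: the Copenhagen Burnout Inventory, the SCIDS, the Minnesota Satisfaction Questionnaire (short form) and the ADQ. The ADQ carries the label "Attitudes towards People with Dementia". No other staff scale is described as an attitude measure.

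The end-of-study list in the same section has residents repeat the quality of life and response behavior measures used at baseline. Staff have two tasks: an ADCS-ADL sheet about each of their residents, and an interview: "Participating staff will undertake a 5 min exit interview at the conclusion of the trial".

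Section IX words the staff-side result differently, as staff reporting that tasks have become easier. It names no staff scale. It also contains a general sentence that outcome measures will not differ between baseline and intervention, and then turns to the ADL score sheets.

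**The concern.** A measured shift needs the same thing measured at least twice in the same people. The plan collects a suitable first score and, on its own schedule, never collects the second. At the end the sponsor could report what staff said during and after the intervention, but could not set it against the attitude score already in hand. A missed end-of-study administration cannot be made good afterwards.

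The difference in wording between V.d and IX adds to the problem. Attitudes towards people with dementia and perceived ease of a task are different constructs. With neither tied to an instrument, the outcome that counts as success could be settled after the data are seen.

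**Working it through.** The main check is a comparison of the schedule with the outcome list. No figure in the plan is in dispute.

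**Step 1. Trace the staff scales.** All four appear in the baseline list in Section VI.c.ii. None appears in the intervention-phase lists, the end-of-study list, the training section (VI.c.iii) or Section IX. Scheduled administrations after baseline: 0 of 4.

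**Step 2. Look for another source of a before/after staff attitude score.**

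| Source | What it gives | Matched staff attitude score? |
|---|---|---|
| ADL web form, both phases | "Subject's attitude to the activity (Likert scale of 1- 4", which concerns the resident | No |
| End-of-shift questionnaire, intervention phase only | "measures tolerance and acceptance of DevaWorld" and "records observations of resident's post and pre-post disposition" | No |
| Interview at the training session, before the intervention | Barriers to taking part or adhering | No |
| End-of-shift notes, intervention phase | Changes staff made to their practice | No |
| ADCS-ADL sheet, end of study | Staff rating of the resident | No |
| Exit interview | Qualitative; covers concerns across the study, including pre-post ones | No |

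**Step 3. What a repeat would deliver.** The number of staff is not stated, so it is inferred from the workload figures in Section VI.c.ii.

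- Residents per staff member: 8 sessions per week / 2 sessions per resident per week = 4. The specimen schedule, which shows residents A to D, agrees.
- Staff: 40 / 4 = 10 for the enrolment target, or 32 / 4 = 8 for the number expected after dropout, if staff fall in proportion to residents.
- 95% half-width for the mean paired change, in SD of change: t(0.975, n−1) / √n.
  - n = 10: 2.262 / 3.162 = 0.715, about 0.72.
  - n = 8: 2.365 / 2.828 = 0.836, about 0.84.
- Change detectable with 80% power by a one-sided t-test, the type named in Section IX: about 0.85 SD (n = 10) or 0.98 SD (n = 8). This assumes alpha 0.05, which is not stated beside the test.

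These numbers support an estimate with an interval, not a significance test. Section VI.c.ii asks only that dyads stay as nearly the same as practical, so there may be fewer complete pairs and a wider interval.

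**Step 4. ADL completion (minor).** The hypothesis in V.d concerns completion of actual ADLs. The baseline ADL form has an explicit item on whether the activity was completed. The intervention form lists a checklist of the ADLs done, with start and finish times, but not that item. The only completion rate that Section IX defines is the percentage of dyads finishing all eight weeks.

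**The case against.** The strongest reply is the general sentence in Section IX that measures will be the same in both phases. It follows directly on the Aim 2 paragraph that contains the staff outcome, and it could be read as an intention to repeat everything. It deserves weight, but it does not close the gap: it names no staff scale and no time point, the text after it is about ADL score sheets, and the specific end-of-study list omits the staff scales. If the sponsor did intend a repeat, the schedule still needs the same edit.

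Second, this is a mixed-methods feasibility study, and not every secondary outcome needs a score. Staff are interviewed before the intervention and at exit, and the exit interview expressly takes in pre-post concerns. Section IX's wording about ease is a retrospective comparison that a single question could answer, though subject to recall. This stands in part. A reader might infer that the study will learn nothing about staff attitudes, or that the outcome cannot be addressed at all. The documents do not support that, because qualitative evidence is planned. What is missing is a matched score.

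Third, V.d does not tie the outcome to the ADQ. That link is an inference from the scale's label, so the sponsor must first state the construct.

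On ADL completion, a reader might infer that completion goes unrecorded during the intervention. That is also too strong. The checklist is a partial record, usual end-of-shift reporting runs in both phases, and the same-measures sentence bears most directly on these forms. At most, two item lists do not match.

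**Conclusion.** The mismatch holds. As scheduled, a listed secondary success outcome has one measurement of the only staff attitude scale, and the plan cannot yield a paired staff attitude score. Section IX's general sentence leaves it open whether this is an omission from the schedule or a difference of intent, and the two places need to be reconciled.

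The consequence is limited. This is one of five secondary outcomes, and nothing here affects the primary outcomes. Even with a repeat, the inferred 8 to 10 staff would give a 95% half-width of about 0.72 to 0.84 SD of change, enough for description only. Those figures rest on the inferred workload of four residents per staff member and on complete pairs. The scheduling finding rests on neither.

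It is worth correcting before end-of-study data collection, because the edit is small and the loss is permanent. The ADL completion point is a minor matter of form wording.

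**What to change.** 1. State what the staff attitude outcome refers to, and use one wording in V.d and IX.
2. Add the ADQ to the end-of-study staff list in Section VI.c.ii. In Section IX, specify the mean paired change with a 95% confidence interval, reported descriptively, for staff with both scores, and give the number of pairs.
3. If the ADQ is not repeated, label the outcome qualitative, name the interviews as its source, and do not claim a measured shift. The same applies if the task-ease wording is the one kept, since the ADQ does not measure that.
4. Make the general same-measures sentence in Section IX agree with the schedule by naming the measures it covers.
5. Minor: put the baseline form's completion item on the intervention ADL form too, and report the proportion of ADLs completed alongside ADL time.

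Cost: one further administration of a questionnaire already in use, by an inferred 8 to 10 staff (its length is not given), with the low precision shown above; one item on an existing web form; and wording edits. Labelling the outcome qualitative needs no extra data collection, but gives up any measured before/after comparison.
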